Standardized Alcohol Cue Exposure Protocol used in Peter Boris Centre for Addictions Research

Approximate Duration: 20 minutes per condition (5 minutes preparation/instruction; 5 minutes exposure; 10 minute assessment); 40 minutes total for neutral + alcohol cue exposure

Note: Participants will be observed for compliance and completion via a video monitoring system installed in both rooms that feeds to a computer monitor located in an adjacent control room. Participants are not permitted to walk behind the bar and drink/interact with any of the alcohol stimuli.

Imaginal Script Methodology

The standard alcohol cue exposure protocol involves direct exposure to personally relevant alcohol cues, including visual, olfactory, gustatory, tactile, and proprioceptive cues. This involves preparation of the participant's typically consumed alcoholic beverage in front of the participant. The alcoholic beverage is a standard size beer (12oz.), glass of wine (5oz.), or mixed drink containing one shot (1.5oz.) of liquor. The beverage is presented in a prototypical glass for the type of alcohol provided (e.g., pilsner glass for beer, stemware for wine). The alcohol cue exposure is typically preceded by a neutral cue exposure involving a glass of water. The order of the exposures is typically not counterbalanced (i.e., neutral first, alcohol second) due to carryover effects from the alcohol cue exposure.

Following preparation of the beverage, the participant is given brief instructions on the inhalation procedure. This involves instructing the participant to pick up the drink and hold the glass 1/2 inch from their nose. They are asked to take five deep breaths and inhale the smell of the drink.

Next, the participant is instructed to put on a pair of headphones and listen to a pre-recorded audio script directing the cue exposure. The experimenter then leaves the room and the participant starts the recording (or the recording can be started by a staff member in an adjacent control room). The audio instructions repeatedly ask the participant to raise the beverage up to their nose and to take five inhalations of the smell of the beverage (total olfactory exposure = ~20s).

The same imaginal script will be used for both neutral (control) and alcohol cues. The methodology for the script is presented below. The duration of the scripts is approximately 3 minutes. The induction is 238 words and written at the 2nd grade level of reading comprehension.

Imaginal Script Structure

1. Introduction and instructions.
2. Initial olfactory exposure; ~5s direct olfactory exposure.
3. Second olfactory exposure; ~5s direct olfactory exposure.
4. Third olfactory exposure; ~5s direct olfactory exposure.
5. Fourth olfactory exposure; ~5s direct olfactory exposure.
6. Concluding instructions.

Imaginal Script Delivered by Audio Recording

"In a moment, I'm going to ask you to smell the beverage in front of you. When you are asked, please take five deep breaths inhaling the smell of the drink.

[7 seconds]

Please pick up the drink and take five deeps breaths, inhaling the smell of the drink with each breath. Keep the drink up to your nose. Take deep breaths and inhale the smell of the drink. Notice the how the glass feels in your hand and the color of the beverage. After you've taken five deep breaths, put the drink back down.

[7 seconds]

Please pick up the drink and take five deep breaths of the drink. Take your time and take deep breaths. Pay attention to the smell of the drink. Once you've taken five deep breaths, put the drink back down.

[7 seconds]

Please pick up the drink and take five deeps breaths, inhaling the smell of the drink with each breath. Keep the drink up to your nose. Take deep breaths and inhale the smell of the drink. Notice the how the glass feels in your hand and the color of the beverage. After you've taken five deep breaths, put the drink back down.

[7 seconds]

Please pick up the drink and take five deep breaths of the drink. Take your time and take deep breaths. Pay attention to the smell of the drink. Once you've taken five deep breaths, put the drink back down.

[7 seconds]

Please remove your headphones now.

Sample Step-by-Step Instructions

Note: The experimenter script is essentially identical for neutral and alcohol cue exposure. The key difference is the beverage that is prepared and presented to the participant. However, the experimenter should refer to the cues as “beverage” or “drink” and not “beer/wine/water/etc”. Instructions/actions are presented in bold; verbal script is presented in italics. E = experimenter.

Prior to start of exposure protocol: Experimenter should ensure that both rooms are set up properly and that all beverages are out on the table/bar. Prepare audio recording on iPad or computer (also check volume level). Prepare iPad REDCap survey and any other assessments prior to participant arriving in cue exposure room.

E: *Now we're going to do the portion of the study that has various environmental cues. I'm going to take you to different rooms in the lab.*

Escort participant to the neutral cues room or bar laboratory

E: *I'm going to give you a moment to get situated (Time 60 seconds, then return). In a little while you will be asked to listen to a recording using these headphones. We will play the recording using the iPad. All you have to do is put on the headphones and press play when instructed to do so.*

Open and pour the beverage (water) into the glass while SLOWLY saying the following:

*We will be using this beverage in this part of the experiment. However, it is important that you NOT drink the beverage under any circumstances. In a little while you will be asked to listen to the recording using the headphones. It is very important to listen carefully to the scene described in the recording and follow the instructions exactly. In addition to asking you to imagine certain things, the recording will ask you to inhale the smell of the beverage from time to time. I'd like to go through smelling the drink with you once before we go any further. Please pick up the drink and hold it a half an inch away from your nose. That's right (**when they complete it**). Now, please take five deep breaths and inhale the smell of the beverage. When you have taken five deep breaths, put the glass back down.*

Pause and count or at least wait until they are ready for the next instructions.

In a moment, I am going to ask you to put on the headphones and the recording will begin soon after. Please be sure to follow the instructions in the recording exactly, but do not drink any of the beverage under any circumstances.

Do you have any questions about anything I've told you so far? Answer any questions.

Now, I'm going to leave the room. Once I've gone, please put on the headphones and press play on the iPad to start the recording.

Leave room and close door. Confirm that participant has put on headphones and started recording. Monitor participant on video screen for compliance and completion of exposure activities. After the recording finishes and subject removes the headphones, enter room and administer assessment.

Procedures for Participants who Consume Alcohol during Session

Alcohol consumption is strictly prohibited in the *Brain Responses to Environmental Influences on Drinking Decisions* study. Participants are not allowed to consume the alcoholic beverage used during the cue exposure. They are also not permitted to go behind the bar and handle or drink any of the alcohol stimuli.

Nonetheless, it is possible that participants may violate study protocol and consume alcohol during the session. Importantly, the amount of alcohol that participants could potentially consume by drinking the cue exposure beverage is relatively modest (1 standard drink) given that participants will all be heavy drinkers who often consume much larger quantities of alcohol as part of their usual drinking patterns.

We will reduce risk of alcohol consumption and intoxication by reminded participants of the alcohol policy during the telephone screening interview, on the consent form, and during the cue exposure in the bar laboratory. We will also monitor participants via the closed circuit video camera system located in the adjacent lab room. This will allow research staff to intervene almost immediately after a participant begins to drink any alcohol.

In the unlikely event that a participant breaks protocol and consumes alcohol, the following procedures should be implemented:

1. Inform the study LPI ([name]) as soon as possible.
2. Remind the participant that alcohol consumption is not permitted and ask them to stop. If they refuse and continue to drink the alcohol, do not intervene further as this may put yourself or the participant at greater risk.
3. The testing session will be terminated immediately as participants will have violated study protocol.
4. If participants consume alcohol, research staff will monitor their blood alcohol concentration via a breathalyzer device. The participant will be asked to remain in the lab until their BAC is below 0.04 g%, which is the recommended safe level for departure from a research study per National Institute on Alcohol Abuse and Alcoholism's Recommended Guidelines for Alcohol Administration Studies.
5. Arrangements should be made for safe transportation home for the participants, including calling for a ride from a friend or family member or calling a taxi.
6. If participants refuse to remain in the lab and have a BAC > 0.04g%, hospital security will be notified and they will handle the situation.
7. If, at any time, participants become agitated, argumentative, violent, or pose any risk to the safety of staff or themselves, research staff should activate their personal alarms (signaling a Code White in the hospital) or contact the security office at [name].

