2) **Risks associated with exposure to alcohol-related cues:** The cue exposure involves exposure to several types of alcohol-related stimuli (visual cues, olfactory cues, imaginal cues). Exposure to these cues could trigger relapse or increased desire to drink in individuals who are in treatment or in recovery for alcohol-related problems. To minimize this risk, any participants who report seeking treatment for alcohol use disorders will be excluded. In addition, any participants who report actively trying to stop or cut down drinking will also be excluded.

3) **Risks associated with consuming alcohol against study protocol:** While it is highly unlikely based on the PI's previous experience conducting similar alcohol cue exposure studies, it is possible that participants may violate study protocol and drink alcohol and become intoxicated during the cue exposure portion of the screening session. This could result in increased risk to the safety of the participant, staff, and the public. We will implement a number of safeguards to mitigate this risk. These safeguards are described in detail in Appendix B and summarized here. First, the study policy prohibiting alcohol consumption will be explained and reiterated multiple times throughout the study (telephone screening, informed consent, cue exposures). Second, while in the bar lab, participants will be monitored by research staff from an adjacent control room via a closed circuit video system. This will allow research staff to immediately intervene in the event that a participant goes behind the bar and attempts to consume the alcohol stimuli. If the participant violates instructions and drinks the prepared beverage used in the cue exposure, the amount of alcohol that they would consume is likely less than they typically consume (i.e., all participants will typically drink heavily on a regular basis). Nonetheless, if a participant does become intoxicated during the session, the procedures outlined in Appendix B will be implemented.

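### Appendix B step 4 lets a participant who has drunk leave once BAC is below 0.04 g%, without a minimum wait or a check that BAC has stopped rising (minor participant-safety point)

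*Protocol*

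**What the plan says.** Appendix B of the protocol covers participants who drink during the cue-exposure session. Under step 4, "research staff will monitor their blood alcohol concentration via a breathalyzer device", and "The participant will be asked to remain in the lab until their BAC is below 0.04 g", the unit being g%. The step attributes the 0.04 g% level to a NIAAA guideline. Neither document states a wait after the last drink, a reading interval, a second reading or a direction of change.

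Other provisions that bear on the point:

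- **Starting level.** Table 1 (exclusion 10) and Section VII (Breathalyzer Test & Urine Screen) require 0.00 at the start of a visit.
- **Amount.** Appendix B gives the cue beverage as one standard drink. Appendix A gives the sizes: 12 oz beer, 5 oz wine or 1.5 oz liquor. Section V says the bar room holds alcohol bottles.
- **Refusal.** Step 2: "If they refuse and continue to drink the alcohol, do not intervene further".
- **Supervision.** Section IX item 3 says of the video link: "This will allow research staff to immediately intervene in the event that a participant goes behind the bar". Appendix B adds: "This will allow research staff to intervene almost immediately after a participant begins to drink any alcohol".
- **Reliance on the appendix.** Section IX item 3 calls the event highly unlikely, but says that "if a participant does become intoxicated during the session, the procedures outlined in Appendix B will be implemented".
- **Leaving.** Step 5: "Arrangements should be made for safe transportation home for the participants", with no BAC condition. Step 6 calls security only if a participant refuses to stay with BAC above 0.04 g%. Step 7 covers any safety risk at any time.

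**The concern.** A rule of the form *stay until below X* suits someone who is already above X and falling. Step 4 applies to someone who started at zero, was seen drinking and had the session stopped at once (step 3). The first reading may therefore come during absorption, when the level is below 0.04 g% only because it has not yet risen. On its wording the rule is then already met.

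What is at stake is the safety of a rare participant who leaves supervision while BAC is still climbing towards or past the level the step guards against. No outcome, sample size or analysis is involved.

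**Working it through.** There is no plan figure to reproduce: 0.04 g% is a fixed cut-off. The check asks whether BAC can be below 0.04 g% at an early reading and reach it later.

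**Inputs from the protocol.** Threshold 0.04 g%; start 0.00; one drink in the cue beverage; 1.5 oz liquor.

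**Assumed inputs (none is in the documents).** Liquor at 40%, so 44.4 mL × 0.40 × 0.789 = 14.0 g alcohol per drink. One compartment. First-order absorption *ka* of 3, 6 or 12 per hour. Elimination β of 0.010, 0.015 or 0.020 g% per hour. Body weight *w* and distribution factor *r*: 55 kg with 0.55, or 80 kg with 0.68. That is 3 × 3 × 2 = 18 settings per dose, and 36 for two and three drinks together. Intake is at once, or at a constant rate over 5, 15 or 30 minutes.

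**Formula for intake at once.** C0 = 100 × grams / (1000 × w × r), and BAC(t) = C0 × (1 − exp(−ka × t)) − β × t. The peak is at t = ln(ka × C0 / β) / ka.

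**One drink, highest case** (55 kg, ka 12, β 0.010). C0 = 1400 / 30250 = 0.0463. Peak time = ln(12 × 0.0463 / 0.010) / 12 = 0.335 h. Peak = 0.0463 × 0.982 − 0.0033 = 0.042 g%. Over the 18 settings, one drink reaches 0.04 g% in 2, 1, 1 and 0 for intake at once or over 5, 15 or 30 minutes.

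**Two drinks, worked example** (60 kg woman, r 0.55, ka 4, β 0.015). C0 = 2800 / 33000 = 0.0848.
- At 5 minutes: 0.0848 × 0.2835 − 0.0013 = 0.023.
- At 10 minutes: 0.0848 × 0.4866 − 0.0025 = 0.039.
- Peak at ln(4 × 0.0848 / 0.015) / 4 = 0.78 h (47 minutes): 0.0848 × 0.956 − 0.0117 = 0.069.

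A reading at 5 or 10 minutes meets step 4, although the peak is well above it.

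**Two and three drinks, counts out of 36 settings.** *Premature* means below 0.04 g% at the reading and at or above it later.

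| Check | At once | 5 min | 15 min | 30 min |
|---|---|---|---|---|
| Below 0.04 at last sip, reaches it later | 32 | 29 | 17 | 9 |
| One reading at 5 min premature | 20 | 15 | 8 | 4 |
| One reading at 15 min premature | 5 | 4 | 0 | 0 |
| One reading at 20 min premature | 1 | 1 | 0 | 0 |
| One reading at 30 min premature | 0 | 0 | 0 | 0 |
| Two-reading rule (see fix) premature | 0 | 0 | 0 | 0 |

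**Sensitivity to slower absorption** (ka 2, 4 or 6; β 0.015; intake at once).
- 60 kg woman, 1.5 drinks: peaks at 0.040 to 0.053, below 0.04 for the first 11 to 59 minutes. The 59 belongs to the case that only just touches 0.040.
- 60 kg woman, two drinks: peaks at 0.059 to 0.074, below 0.04 for the first 7 to 23 minutes.
- 80 kg man, two drinks: peaks at 0.030 to 0.041, so only about at the threshold.
- 80 kg man, three drinks: peaks at 0.052 to 0.066, below 0.04 for the first 8 to 28 minutes.

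**Why the two-reading rule gives zero.** After the last sip the modelled curve has a single peak. If a later reading is not higher than an earlier one, the peak has passed, so a level below 0.04 g% then stays below it. With exact readings this holds for any single-peaked curve, whatever *ka* is.

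**The case against.** The strongest case is that step 4 already means what it should. Monitoring a level until it is below a threshold naturally describes following it down, and a rule satisfied at the first sip would have no purpose. That is a sensible reading and competent staff may well apply it. But it is not written, and the appendix is an instruction to research staff dealing with an uncooperative participant.

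Second, the window is short and a wait alone nearly closes it: no single reading at 30 minutes is premature in the 36 settings. This stands. It limits the size of the point, and a plain 30-minute wait would be a reasonable alternative. The step contains no wait either, and the trend condition also covers slower absorption.

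Third, early figures are modelled blood levels. Mouth alcohol could raise an early breath reading, which works against a falsely low result. This stands too, and is a reason to delay the first reading.

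Fourth, much of the harm is covered elsewhere. Live video allows quick intervention, transport home is arranged at any BAC, and step 7 applies at any time. This stands, although transport does not observe someone who is still absorbing alcohol.

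Fifth, the participant most likely to drink two or three drinks is one who ignores instructions. Someone at 0.03 g% and rising who walks out still does not trigger step 6. This stands: the change helps only those who agree to stay.

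A reader might infer that the one-drink cue beverage itself makes step 4 unsafe. The model does not support that, since only 2 of 18 settings reach 0.04 g% even when it is drunk at once. A reader might also infer that the protocol provides for release on one reading, or departs from the guideline it names. The wording suggests repeated readings, and the guideline is not available here to check.

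**Conclusion.** The gap is real and minor. As worded, step 4 can be met before BAC passes 0.04 g%, mainly within the first 15 to 20 minutes after rapid intake of about 1.5 to 2 drinks in a light woman or 2 to 3 in an average man. The protocol foresees how more than one drink could be taken (refusal under step 2, access to the bar stock), but it states no such amount, so those doses are assumptions.

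The counts are unweighted tallies over chosen settings. They are not probabilities of release, and they are conditional on an event that the protocol calls highly unlikely. The textual finding does not depend on the model; its size does. The point is worth a cheap edit and has no bearing on the aims or the statistical analysis.

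**What to change.** Reword step 4 so that departure needs two breath readings: the first at least 15 minutes after the last drink and the second at least 15 minutes later, both below 0.04 g% and the later not higher than the earlier. Otherwise repeat every 15 minutes until a consecutive pair meets this. The 15-minute values are assumed defaults, to be lengthened if the device instructions require it. Keep the 0.04 g% threshold and steps 5 to 7.

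The cost is one sentence, using the breathalyzer and monitoring already in place. The downside is a longer stay: in the model, release comes 30 to 75 minutes after the last sip of one drink, and 30 to 45 minutes after a quarter of a drink, although nearly all one-drink settings never reach the threshold. Staying remains a request, as it is now.

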## Final Statistical Analysis Plan

### Data Analysis

#### Behavioral analyses.

Individual APT trials were coded according to the method used in MacKillop et al. (2014). Inelastic choices were choices for a participant's personal maximum consumption. Elastic choices were choices in which consumption was less than maximum but greater than zero. Suppressed choices were choices for no alcohol. Observed alcohol demand indices included Intensity (consumption at free price), Breakpoint (price that suppressed consumption to zero), and Omax (maximum expenditure). An exponentiated demand curve model (Koffarnus et al., 2015) was used to estimate  $\alpha$  for each participant's mean neutral and alcohol demand curves. A shared  $k$  parameter was calculated as the logarithmic range in consumption ( $k = 2.23$ ). A small number of outliers were winsorized for Omax (3 datapoints) and  $\alpha$  (3 datapoints) (Tabachnick and Fidell, 2001). Omax was square root transformed and  $\alpha$  was logarithmically transformed to correct for skew. Four participants did not reach breakpoint and were excluded from analyses using this index.

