The current study will extend these initial findings by examining the neural correlates of changes in alcohol demand via an experimental manipulation that models motivational factors in real-world drinking decisions. We hypothesize that acute increases in alcohol value will be subserved by changes in areas associated with reward salience, interoceptive processing, and perceived value. Furthermore, the proposed studies will include both males and females allowing for systematic examination of sex differences. Finally, the study will examine whether severity of alcohol misuse moderates behavioural and neural responses to the alcohol cues.

III. Purpose

The core scientific purpose of this project is to use our novel fMRI paradigm to investigate the neural correlates of increases in alcohol demand resulting from exposure to alcohol cues. The specific aims are as follows:

Primary Aim #1: Characterize neural activity associated with increases in alcohol demand resulting from exposure to alcohol cues. Hypothesis: Increases in alcohol value following alcohol cues will be associated with significant increases in activity in ventral striatum, anterior insula, and posterior cingulate.

Secondary Aim #1: Investigate severity of alcohol misuse as a moderator of the manipulations. Hypothesis: Based on previous behavioral findings, we predict that increased AUD severity will enhance reactivity to cues both in terms of behavioural response and brain activity associated with alcohol decisions.

Secondary Aim #2: Examine patterns of functional connectivity underlying alcohol demand. Based on recent evidence supporting network-based perspectives in the neuroscience of decision making, we will conduct functional connectivity analyses to characterize the underlying neural networks that subserve alcohol demand in general and alterations in connectivity from the alcohol cue exposure.

IV. Design

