Alcohol Demand	Alcohol Purchase Tasks-State Versions (e.g., “how many drinks would you consume right now if they cost \$3 each?”. All choices are hypothetical.)	REDCap
Alcohol Craving	Craving visual analog scales (e.g., three items assessing subjective alcohol craving; “How much do you want a drink?” “How high is your urge for a drink?” and “How much do you crave a drink?”; Rated from 0-100)	REDCap
Subjective Affect	Six 100-point affect circumplex items, from -50 to +50: Tense-to-Calm, Sad-to-Happy, Nervous-to-Relaxed, Bored-to-Excited, Stressed-to-Serene, and Depressed-to-Elated.	REDCap
Physiological Arousal	Blood pressure; heart rate	Electronic blood pressure monitor

Functional Magnetic Resonance Imaging (MRI) Scan

[figure not shown]
Participants will undergo a 60-minute fMRI scan at the Imaging Research Centre at SJHH on a research-dedicated 3-Tesla General Electric Discovery 750 MRI system. Scans will be administered by a licensed MRI technologist at the IRC.

1. Functional imaging will comprise T2*-weighted echo planar imaging scans with a gradient echo pulse sequence.
2. Structural imaging will comprise high-resolution T1-weighted fast spoiled gradient echo scan
3. Resting state functional connectivity scans will comprise T2*-weighted echo planar imaging scans with a gradient echo pulse sequence.

[figure not shown]
The in-scanner behavioural task is our fMRI alcohol demand paradigm (Alcohol Purchase Task; APT). A schematic depiction of the paradigm is presented in **Figure 1**. On each trial, participants are asked how many standard-sized drinks of their preferred alcoholic beverage that they would consume at a range of prices (e.g., “How many drinks would you consume if they cost \$4 each?”). Each run will comprise 22 trials in a randomized order. An important aspect of the paradigm is its fractionation of the choice process into two discrete units: a stimulus processing Consider period (4 sec) and an active selection Choose period (<6s). In the Consider epoch, participants process the drink price for that trial and mentally decide how many drinks they want to purchase. In the Choose epoch participants’ behaviorally select their consumption level. This permits dissociation of the cognitive processing part of the decision from the motor response of inputting the choice. The Consider period is considered the

primary period of interest. A jittered inter-stimulus interval (ISI) screen is presented in between trials (M = 8 sec, range 1-15sec)¹⁴.

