#### Statistical Analyses for Behavioral Data

Differences in alcohol demand were analyzed using separate repeated measures analyses of variance (ANOVA) models for each demand index. In these models, condition was a two-level within-subjects factor (neutral, alcohol). Partial eta-squared was calculated as a measure of effect size. Subjective craving was similarly analyzed using a repeated measures ANOVA. A conventional significance level of  $p < .05$  was used for all analyses.

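### Excluding the four participants who never reached breakpoint selects on the outcome; without the condition in which this happened, the direction of the effect on that index cannot be told (minor)

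*SAP*

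**What the plan says.** In the in-scanner purchase task (Protocol VII, fMRI scan), participants state the number of "standard-sized drinks of their preferred alcoholic beverage that they would consume at a range of prices". On size the Protocol says only: "Each run will comprise 22 trials in a randomized order". The highest price is not given in the text.

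The SAP (Behavioral analyses) defines the index as "Breakpoint (price that suppressed consumption to zero", and then states: "Four participants did not reach breakpoint and were excluded from analyses using this index". The same paragraph gives transformations for Omax and alpha but none for Breakpoint.

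The SAP (Statistical Analyses for Behavioral Data) uses "separate repeated measures analyses of variance (ANOVA) models for each demand index". On the factor it says: "In these models, condition was a two-level within-subjects factor (neutral, alcohol". On effect size: "Partial eta-squared was calculated as a measure of effect size".

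Neither document says in which condition(s) the four failed to reach breakpoint, how many participants were analysed, or whether any analysis retained the four.

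**The concern.** By the SAP's own definition, a participant who never chose zero has a breakpoint above the top price. That is partial information about a high value. Removing such people drops cases because of the outcome being analysed, from the upper end of demand. The model needs a pair of values, so a participant censored in one condition also loses the value observed in the other.

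At stake is the cue effect on Breakpoint, one of four demand indices (Intensity, Breakpoint, Omax, alpha). The Protocol expects demand to rise after alcohol cues. If that is so, some of the four may be the people in whom the cue raised Breakpoint most.

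**Working it through.** **1. The plan's own figure.** Protocol VI (Sample Size) gives N = 70, f = .35, alpha = .05, power .80. With sex as a two-group factor, lambda = f²(N − 2) = 0.1225 × 68 = 8.33 on 1 and 68 df gives power .812, and the smallest adequate N is 68. As one group, lambda = 0.1225 × 70 = 8.575 gives power .823 (smallest N 67). The planned size is not in question.

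**2. Inputs.** From the documents: four excluded, which is 4/70 = 5.7% of the planned sample or 4/77 = 5.2% of the oversampled one. Assumed: N = 70 (analysed N not stated), f = .35 read as mean difference over SD of differences (dz), between-condition correlation r = .5 to .9, and a constant cue shift.

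**3. Model.** The neutral value is a standard normal. The alcohol value has correlation r with it and is shifted by .35 × √(2(1 − r)), because the SD of the difference is √(2(1 − r)). The ceiling is set so that 4/70 of participants exceed it in at least one condition. Exclusion keeps only pairs with both values below it. Results are simulated, with 2 to 3 million draws per setting.

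**4. Log-type (normal) scale.** F = N·dz², and partial eta-squared = N·dz² / (N·dz² + N − 1). With all 70: 8.575/(8.575 + 69) = 0.111, power .823.

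| r | mean effect, excluded/latent | dz | partial eta-squared, n = 66 | power |
|---|---|---|---|---|
| .5 | 0.93 | .337 | 0.103 | .77 |
| .7 | 0.95 | .342 | 0.106 | .78 |
| .9 | 0.97 | .345 | 0.108 | .79 |

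Going from 70 to 66 alone would give power .80, so about .02 of the loss is sample size.

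**5. Untransformed skewed scale.** Same model, lognormal breakpoint, analysed raw. Ranges run over r = .5 to .9.

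| log SD | mean effect, excluded/latent | dz, latent to excluded | partial eta-squared, latent to excluded |
|---|---|---|---|
| 0.4 | 0.84-0.90 | .321-.327 to .324-.328 | 0.095-0.098 to 0.096-0.098 |
| 0.7 | 0.76-0.81 | .270-.286 to .300-.305 | 0.069-0.077 to 0.084-0.086 |
| 1.0 | 0.66-0.71 | .211-.229 to .270-.277 | 0.043-0.051 to 0.069-0.072 |

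The mean difference shrinks more here, but exclusion also trims the variance, so the standardised effect is unchanged or higher than latent. Power follows lambda = N·dz². At r = .5 and log SD 0.4 it goes from 70 × .327² = 7.49 to 66 × .324² = 6.93, a small fall. At log SD 0.7 it goes from 70 × .286² = 5.73 to 66 × .305² = 6.14, a rise.

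**6. By pattern (normal scale, r = .7).** In units of the SD of differences, the retained mean is .333. Mean over all 70 = (66 × .333 + 4x)/70, where x is the mean of the four.

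- Alcohol only, x = 1.52: (21.98 + 6.08)/70 = .401; ratio .333/.401 = 0.83.
- Both, x = 0.16: (21.98 + 0.64)/70 = .323; ratio 1.03.
- Neutral only, x = −1.18: (21.98 − 4.72)/70 = .247; ratio 1.35.
- Two alcohol only and two neutral only: (21.98 + 3.04 − 2.36)/70 = .324; ratio 1.03.

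Over r = .5 to .9 the three pure patterns give about 0.82-0.84, 1.02-1.04 and 1.33-1.38. In the model the excluded are censored under alcohol only in 40-66% of cases, under both in 10-43%, and under neutral only in 17-24%.

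**The case against.** The best defence is that the exclusion and its count are disclosed, the loss is four people on one index, and the primary aim is neural. In simulation the exclusion analysis does not inflate type I error (0.044-0.049). A natural reading of the SAP sentence is that the four reached breakpoint in neither condition, and for that pattern the effect is roughly nil. All of this stands, and it is why the point is minor. It does not remove the selection on outcome, and the sentence does not settle the condition.

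Four stronger readings are tempting but not supported:

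- **That the reported cue effect is understated.** A reader might infer this because demand is expected to rise after alcohol cues. The average over patterns leans that way, but the SAP gives no condition, and censoring under neutral cues reverses the direction.
- **That partial eta-squared and power are too low.** This holds on a log-type scale only. No transformation is stated for Breakpoint, and on a skewed raw scale partial eta-squared is unchanged or higher than latent. Against coding the four at the top price, exclusion is equal or slightly lower (for example dz .275 against .282 at log SD 1.0, r = .7).
- **That the attenuation is 10-18%.** Such figures need a cue effect that rises with demand by an assumed slope. The Protocol's Secondary Aim #1 says "we predict that increased AUD severity will enhance reactivity to cues both in terms of behavioural response and brain activity", but that concerns severity, not level of demand, and gives no slope.
- **That other results are compromised.** The exclusion is confined to analyses of this index. Whether Omax is itself bounded by the top price is a separate question.

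**Conclusion.** The concern holds as a minor point. The four values are right-censored, and excluding them selects on the outcome. On average the mean cue effect on Breakpoint would keep about 93-97% of its latent value on a log-type scale, and less on an untransformed skewed scale. For these four people the ratio could be anywhere from about 0.82 to about 1.38, depending on a count that the SAP does not give. If all four were censored in both conditions, the effect is close to nil and its sign is not settled.

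The sizes rest on N = 70, f = .35 as a paired effect, r = .5 to .9 and a constant shift. The documents do not supply the analysed N, the correlation, the spread of Breakpoint or the top price. The classification as censored and the selection on outcome do not depend on those assumptions.

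**What to change.** Keep the exclusion analysis as reported. Beside it, labelled post hoc, add text such as:

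*All participants are retained. Breakpoint is treated as right-censored at the highest price in each condition where it was not reached. The cue effect is estimated by a paired (bivariate) censored-normal likelihood with an unstructured 2 × 2 covariance, on a stated log-type scale. Coding censored values at the highest price is a further check. The numbers censored under neutral only, alcohol only and both are reported, with the highest price and the analysis scale.*

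If the analyses disagree on the cue effect, the Breakpoint conclusion should not rest on the exclusion result alone.

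The cost is a three-cell count, one price and one or two extra models on data already held. If only one simple sensitivity analysis is feasible, top-price coding will serve, though it attenuates too (0.96-0.97 of the true effect on the normal scale, and no better than exclusion at r = .9). The censored likelihood is preferred because it recovers 0.99-1.01 of the true effect on that scale, with type I error 0.047-0.052. Its downside is a distributional assumption: on untransformed lognormal data with a constant shift it gives 0.95-0.96 (log SD 0.5) or 0.91-0.92 (log SD 0.75), hence the log-type scale. It is also chosen after the data were seen, so both results should be shown.
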